5.2 Exclusion Criteria

- 1. History of any of the following in either eye:
 - a. Ocular cancer (including melanoma)
 - b. Herpetic keratitis
 - c. Corneal transplant (full-thickness or lamellar)
 - d. Documented and repeated elevated IOP in either eye
 - e. Posterior Polymorphous Corneal Dystrophy (PPCD; aka Schlichting dystrophy)
 - f. Uveitis
 - g. Cataract surgery within the 3 months in prior to Study Day 0
- 2. Refractive surgery in the study eye, including phakic IOL currently in place Note: Potential subjects who have had the phakic IOL placed and removed are allowed. Limbal relaxing incision performed at the time of cataract surgery is allowed
- 3. Any condition that would impair examination of the anterior chamber structures in the Study Eye
- 4. Anterior Chamber IOL placement (in the Study Eye)
- 5. Expected or planned ocular surgery (incisional or laser) in the Study Eye within the next 3 months (including endothelial keratoplasty)
- 6. Use of systemic or dermatological cytotoxic chemotherapy within the 1 month prior to or planned use within the 3 months following Study Day 0

Trefoil Therapeutics, Inc.	Clinical Study Protocol TTHX-001
Confidential and Proprietary	Amendment 1.0: September 8, 2020

- 7. Use of hypertonic saline eye preparations (e.g.; Muro 128) within the 3 days prior to Study Day 0 (either eye)
- 8. Active extra-ocular inflammation from any non-infectious or infectious cause (bacterial, viral or fungal) in the Study Eye within the 6 months prior to Study Day 0

Note: Mild blepharitis and/or dry eye related inflammation are allowed

- 9. Treatment with a rho kinase inhibitor within the last 3 months (either eye)
- 10. Use of cyclosporine ophthalmic emulsion (e.g.; RESTASIS®) within the 30 days prior to Study Day 0 (either eye)
- 11. Use of Xiidra® (lifitegrast ophthalmic solution) within the 30 days prior to Study Day 0 (either eye)
- 12. Systemic (nasal, inhaled, oral, parenteral, or topical) or ophthalmic corticosteroid use in the 30 days prior to Study Day 0 unless approved by the Medical Monitor

Note: Potential subjects on a stable chronic low-dose that is not expected to change in the 3 months following Study Day 0 may be considered for the study after approval by the Medical Monitor

13. History of significant allergy, hypersensitivity, or intolerance to any drug compound, food, or other substance

Note: This includes all components and excipients of the study drug

- 14. Women of childbearing potential who are currently pregnant, breast feeding, planning to become pregnant during the study, or not willing to use highly effective birth control measures (e.g., hormonal contraceptives [oral, implanted, transdermal], or mechanical barrier methods [spermicide in conjunction with a barrier such as a condom or diaphragm], or intra-uterine device [IUD]) during the entire course of the study
- 15. Current or recent (e.g., the 30 days prior to Study Day 0) participation in any other, interventional clinical research study
- 16. An employee of the site that is directly involved in the management, administration, or support of this study or be an immediate family member of the same
- 17. Any other reason (e.g., serious systemic disease or uncontrolled medical condition) that, in the opinion of the Investigator could increase the subject's risk, interfere with the interpretation of the study results, or affect the subject's ability to provide informed consent or comply with the study

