	the central reading facility during the screening period
	Note: FECD patients with dense central guttae may not be countable and therefore,
	not eligible
	7. Vision of 20/400 or better, in each eye (BCVA of at least 15 letters (per ETDRS])
	8. Subjects who are women of childbearing potential (WOCBP) must be using an
	acceptable method of birth control [e.g., an Intrauterine Contraceptive Device
	(IUCD), hormonal contraceptives, or double barrier method] starting at least 1
	month prior to Study Day 0 and for the duration of the study. If a female subject is
	currently abstinent, they must agree to use a double barrier method of birth control

Trefoil Therapeutics, Inc. Confidential and Proprietary

	before they become sexually active. Men who are sexually active with a woman of childbearing potential must agree to use a double barrier method.
Exclusio	m
1.	 History of any of the following in either eye: a. Ocular cancer (including melanoma) b. Herpetic keratitis c. Corneal transplant (full-thickness or lamellar) d. Documented and repeated elevated IOP in either eye
	 e. Posterior Polymorphous Corneal Dystrophy (PPCD; aka Schlichting dystrophy) f. Uveitis g. Cataract surgery within the 3 months prior to Study Day 0
2.	Refractive surgery in the Study Eye, including phakic IOL currently in place Note : Potential subjects who have had the phakic IOL placed and removed are allowed. Limbal relaxing incision performed at the time of cataract surgery is allowed
3.	Any condition that would impair examination of the anterior chamber structures in the Study Eye
	Anterior Chamber IOL placement (in the Study Eye)
	Expected or planned ocular surgery (incisional or laser) in the Study Eye within the 3 months following Study Day 0 (including endothelial keratoplasty)
	Use of systemic or dermatological cytotoxic chemotherapy within the 1 month prior to or planned use within the 3 months following Study Day 0
	Use of hypertonic saline eye preparations (e.g.; Muro 128) within the 3 days prior to Study Day 0 (either eye) Active extra-ocular inflammation from any non-infectious or infectious cause
0.	(bacterial, viral or fungal) in the Study Eye within the 6 months prior to Study Day 0
	Note: Mild blepharitis and/or dry eye related inflammation are allowed
	Treatment with a rho kinase inhibitor within the last 3 months (either eye) Use of cyclosporine ophthalmic emulsion,(e.g.; RESTASIS®) within the 30 days prior to Study Day 0 (either eye)

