5.1 Inclusion Criteria

- 1. Male or female, 18 years of age or older
- 2. Able and willing to provide informed consent

Trefoil Therapeutics, Inc.	Clinical Study Protocol TTHX-001
Confidential and Proprietary	Amendment 1.0: September 8, 2020

- 3. Fuchs Endothelial Corneal Dystrophy, pseudophakic bullous keratopathy, or endothelial dysfunction/ insufficiency due to surgical intervention diagnosed more than 6 months prior to Study Day 0 in the study eye
- 4. Intact anterior chamber anatomy (if posterior capsule is open or absent, absence of vitreous in the anterior chamber must be verified or enrollment approved by the Medical Monitor) in the study eye and no structural abnormalities that would make intracameral injection difficult
- 5. Able to obtain clear corneal endothelial cell (CEC) morphology and central CEC counts by specular microscopy from both eyes as determined by the central reading facility
- 6. Central endothelial cell count of < 2000 mm² in at least one eye as determined by the central reading facility during the screening period

Note: FECD patients with dense central guttae may not be countable and therefore, not eligible

- 7. Best Corrected Visual Acuity (BCVA) of at least 15 letters (per Early Treatment of Diabetic Retinopathy Study [ETDRS] testing) (approximately 20/400), in each eye
- 8. If female, are non-pregnant, non-lactating Subjects who are women of childbearing potential (WOCBP) must be using an acceptable method of birth control [e.g., an Intrauterine Contraceptive Device (IUCD), hormonal contraceptives, or double barrier method] starting at least 1 month prior to Study Day 0 and for the duration of the study. If a female subject is currently abstinent, they must agree to use a double barrier method of birth control before they become sexually active. Men who are sexually active with a woman of childbearing potential must agree to use a double barrier method.

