6.3 Concomitant Medications and Treatments

6.3.1 Concomitant Medications

Subjects are expected to receive concomitant medications for the management of concurrent medical conditions. Medications taken during the 28 days prior until 28 days following the last study treatment administration will be recorded. Artificial tears are allowed during the study but other ocular medications must be discussed with the masked Medical Monitor.

6.3.2 **Prohibited Medications**

The following medications are prohibited:

Trefoil Therapeutics, Inc.	Clinical Study Protocol TTHX-001
Confidential and Proprietary	Amendment 1.0: September 8, 2020

- Rho-kinase inhibitors (topical or systemic, e.g.; Fasudil, Netarsudil [Rhopressa])
- Systemic or dermatological cytotoxic chemotherapy
- Hypertonic sodium chloride ointment and drops including Muro 128
- Systemic (nasal, inhaled, oral, parenteral, or topical) or ophthalmic corticosteroids **Note:** Inhaled corticosteroids are acceptable as long as the subject is on stable low doses and the dose is not expected to change for the duration of the study
- Cyclosporine ophthalmic emulsion
- Xiidra ® (lifitegrast ophthalmic solution)

Subjects requiring the use of prohibited medications must be discussed with the masked Medical Monitor.

6.3.3 **Pregnancy Testing and Contraception**

Women of child-bearing potential (WOCBP) are defined as a premenopausal female capable of becoming pregnant. Women who are not WOCBP are those who have not had a menstrual cycle for at least 2 years or who have had hysterectomy, bilateral tubal ligation, or bilateral oophorectomy. Sexually active female subjects who are WOCBP must use at least 1 highly-effective method of contraception or at least 2 less effective methods of contraception (including 1 barrier method), starting at least 1 month prior to Day 0, and male subjects who are sexually active with women of childbearing potential must agree to use a double-barrier method of contraception. Per *ICH M3(R2) Non-Clinical Safety Studies for the Conduct of Human Clinical Trials and Marketing Authorization for Pharmaceuticals*, highly-effective methods are defined as "those, alone or in combination, that result in a low failure rate (i.e., less than 1% per year) when used consistently and correctly." FDA-approved contraceptive methods and estimated failure rates are summarized in Table 2.

Method	Failure Rate
Highly-Effective*	
Sterilization surgery for women	Less than 1%

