Sterilization implant for women	Less than 1%
Sterilization surgery for men	Less than 1%
IUD Copper	Less than 1%
IUD with Progestin	Less than 1%
Implantable Rod	Less than 1%
Less-Effective	
Shot/ Injection	6%
 Oral Contraceptives "The Pill" * 	9%
• Patch	9%
Vaginal Contraceptive Ring	12%
Diaphragm with Spermicide	12-24%
Cervical Cap with Spermicide	17-23%
Male Condom	18%
Female Condom	21%
Spermicide Alone	28%

Table 2: FDA-Approved N	lethods of Contraception and Es	stimated Failure Rates
The second secon		

*(including Combined, Extended/ Continuous Use Combined Pill, and the "Mini Pill", Progestin only) Adapted from FDA Birth Control Guide www.FDA.gov/birthcontrol

Trefoil Therapeutics, Inc.	Clinical Study Protocol TTHX-001
Confidential and Proprietary	Amendment 1.0: September 8, 2020

The contraceptive plan for each subject should be discussed with the Investigator and will be determined at the Investigator's discretion including the use of a double-barrier (e.g.; male condom, female diaphragm with spermicide) in male subjects.

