6.4.10 Urine Pregnancy Test

WOCBP must be tested prior to the start of study treatment and after the completion of study treatment to confirm a continued non-pregnant state. Commercially available urine dip-stick pregnancy tests are acceptable.

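### Entry criteria accept the pill or patch as sole contraception, but Section 6.3.3 and Table 2 class both as less effective and require a second method

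*Protocol*

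**What the plan says.** Contraception is set out in three parts of the protocol, two of which are repeated in the synopsis.

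- **Section 5.1, inclusion 8** (and the synopsis): women of childbearing potential "must be using an acceptable method of birth control [e.g., an Intrauterine Contraceptive Device (IUCD), hormonal contraceptives, or double barrier method". Hormonal contraceptives appear without restriction by type and without a second method.
- **Section 5.2, exclusion 14** (and the synopsis): women are excluded if "not willing to use highly effective birth control measures (e.g., hormonal contraceptives [oral, implanted, transdermal". The list goes on to spermicide with a condom or diaphragm, and to the IUD.
- **Section 6.3.3**: sexually active women of childbearing potential "must use at least 1 highly-effective method of contraception or at least 2 less effective methods of contraception (including 1 barrier method". Highly effective methods are defined, by reference to an ICH guideline, as those that "result in a low failure rate (i.e., less than 1% per year) when used consistently and correctly", and the reader is sent to Table 2 for methods and failure rates.
- **Table 2**: "Implantable Rod" is listed as Highly-Effective (less than 1%). "Oral Contraceptives" and the patch are listed as Less-Effective, at 9% each.

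After Table 2, the protocol says that each subject's contraceptive plan is to be discussed with, and determined by, the Investigator. On testing, Section 6.4.10 says women of childbearing potential "must be tested prior to the start of study treatment and after the completion of study treatment to confirm a continued non-pregnant state". The visit lists and Appendix A place those tests at Day 0 and Day 56.

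**The concern.** The protocol uses the term highly effective for two different sets of methods. Exclusion 14 includes oral and transdermal hormones in that set, and Table 2 leaves them out. The label matters because, under Section 6.3.3, it decides whether one method is enough. A site that takes the label from exclusion 14 and applies Section 6.3.3 would conclude that the pill alone suffices. A site that takes it from Table 2 would require a barrier as well.

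Inclusion 8 has a related fault. It speaks of an acceptable method, not a highly effective one, so its conflict is with the two-method rule and not with the label.

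At stake is the protection of women who could become pregnant during repeated intracameral dosing with a drug not previously given to humans. Sites could enroll differently, and a woman on the pill alone could be within the entry criteria while outside the contraception section. The deviation list in Section 10.1.1 names subjects who did not meet entry criteria. Such a woman does meet them, so that item would not flag her.

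**Working it through.** The plan gives no figure to reproduce here. The check sets the texts side by side.

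**Step 1. Classify the methods by the protocol's own table.**

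| Method | Exclusion 14 | Inclusion 8 | Table 2 group | Table 2 rate | Enough alone under 6.3.3? |
|---|---|---|---|---|---|
| Oral contraceptive | highly effective | accepted | Less-Effective | 9% | No |
| Patch (transdermal) | highly effective | accepted | Less-Effective | 9% | No |
| Implant | highly effective | accepted | Highly-Effective | less than 1% | Yes |
| IUD | highly effective | accepted | Highly-Effective | less than 1% | Yes |
| Injection | not named | accepted if hormonal | Less-Effective | 6% | No |
| Vaginal ring | not named | accepted if hormonal | Less-Effective | 12% | No |

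Exclusion 14 names 3 hormonal routes. Two of the 3 (oral, transdermal) are Less-Effective in Table 2, and 1 of the 3 (implanted) is Highly-Effective. The unrestricted wording of inclusion 8 reaches further, to the injection and the ring. Table 2 does not label those two rows as hormonal; treating them so is ordinary usage.

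**Step 2. Take one case through all the rules.** A sexually active woman uses the pill and nothing else.

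- Inclusion 8: met, because she uses a hormonal contraceptive.
- Exclusion 14: not triggered, because the pill is one of its own examples of highly effective contraception.
- Section 6.3.3 with Table 2: not met, because she uses one less effective method where two, including a barrier, are required.

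The patch gives the same result.

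**Step 3. Look for text that settles the conflict.** Section 5 does not refer to Section 6.3.3, and nothing sets an order of precedence. The Investigator-discretion sentence neither moves the pill or patch to another group nor waives the two-method rule.

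**Step 4. Context from the test schedule.** Injections are on Days 0, 7, 14 and 21, and urine tests are on Days 0 and 56. Scheduled tests therefore accompany 1 of 4 injections, and 4 − 1 = 3 injections (Days 7, 14, 21) have none. The next test comes nominally 56 − 21 = 35 days after the last injection. These counts do not measure the conflict. They show only that scheduled testing would not compensate for a missing second method while dosing continues.

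**The case against.** The strongest reply is that the protocol must be read whole. Section 6.3.3 is the dedicated section, its rule is mandatory, and the lists in Section 5 are only examples. Nothing in Section 5 says that one method suffices, so a careful site would require the barrier. That is a fair reading, and it lowers the likely harm. It does not remove the conflict: exclusion 14 does not merely leave out the second method, it gives the pill and patch the very label that makes a second method unnecessary under Section 6.3.3.

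Other points on that side:

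- *The Investigator settles each subject's plan.* This is a real checkpoint, placed next to Table 2, and makes purely mechanical screening less likely. It still leaves the Investigator with two inconsistent definitions.
- *The failure-rate definition assumes consistent and correct use, and Table 2 does not state the basis of its rates.* Correct, so 9% should not be set against the 1% threshold as if both were on the same footing. The conflict does not need that comparison; it rests on Table 2's group headings.
- *The Highly-Effective heading carries an asterisk, and the footnote lists pill types.* The pill row carries the same mark, so the footnote most naturally belongs there. If it were read as making the pill highly effective, Table 2 would contradict its own placement of the pill, and the patch would still be Less-Effective.
- *Test timing is a separate matter.* This stands. The counts would be the same after the wording is corrected. Section 6.6 also asks subjects to report pregnancy promptly and stops study drug permanently if it occurs. Under Section 6.5.10, those who stop early have the Day 56 assessments about 28 days after their last dose.
- *The number of women affected is unknown.* This stands too.

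**Conclusion.** The inconsistency is real and lies in the current text. A sexually active woman on the pill or patch alone satisfies Sections 5.1 and 5.2 and breaches Section 6.3.3. For exclusion 14 the conflict covers 2 of the 3 hormonal routes it names; for inclusion 8 it extends to the injection and the ring. Implants and IUDs agree throughout.

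The conclusion rests on Table 2's headings as printed and on the two-method rule being mandatory for sexually active women of childbearing potential. The practical size cannot be stated: the protocol gives neither the number of such women expected nor how many rely on the pill or patch alone, and both may be small. Randomization, endpoints, sample size and analysis are not affected. It is a minor point, but worth correcting because it concerns a safety rule in a first-in-human study.

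**What to change.** In inclusion 8, in exclusion 14 and in both synopsis copies, replace the lists of example methods with one statement: at least one highly effective method, or at least two less effective methods of which one is a barrier, as defined in Section 6.3.3 and Table 2. This also covers the injection and the ring.

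A useful addition is one line at Table 2 saying whether spermicide combinations count as one method or two. The table gives diaphragm with spermicide a single row, which suggests one method. It lists the male condom and spermicide separately, which suggests two. Exclusion 14 offers both combinations as highly effective, so the sponsor should confirm how each counts.

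The cost is wording in four places plus the optional line. Any woman relying on the pill or patch alone would need to add a barrier method, which Section 6.3.3 already asks of her if she is sexually active.

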5.3 Subject Withdrawal Criteria

Subjects will be discontinued from continued study treatment if any of the following occur:

- Intolerable side effects
- The Investigator feels it is in the subject's best interest
- Non-compliance
- Pregnancy

Subjects who are discontinued from study treatment are expected to remain on the study and complete all appropriate safety and efficacy assessments.

Subjects may withdraw from the trial at any time and for any reason.

Trefoil Therapeutics, Inc.	Clinical Study Protocol TTHX-001
Confidential and Proprietary	Amendment 1.0: September 8, 2020

If a subject withdraws from the trial, attempts should be made to contact the subject to determine the reason(s) for discontinuation while respecting the subject's privacy. All procedures and evaluations required by the final study visit should be completed in the event of early withdrawal. All subjects who discontinue the trial due to an adverse event must be followed until the event has resolved, returned to baseline, or stabilized (if resolution is not anticipated).

6. TREATMENT OF SUBJECTS

This study will be conducted at qualified clinical investigational sites. Sites will be selected based on the ability to safely conduct the study and where Trefoil can be assured of patient safety and the ability to effectively monitor. Investigational sites should monitor health websites such as (https://www.cdc.gov/coronavirus/2019-ncov/index.html) for up-to-date information and resources.

Investigational site staff are instructed to follow their institutional infection control standard procedures and to consider additional measures during periods of community transmission of conditions such as COVID-19. These additional measures may include:

- Contacting subjects the day before a scheduled appointment
 - To determine if they are experiencing any signs or symptoms of possible infections, such as
 - Fever
 - Cough
 - Shortness of breath
 - Sore throat
 - To determine if the subject has tested positive for COVID-19, been in contact with someone who is known or suspected COVID-19, or traveled to an area of risk
- Rescheduling subjects who are experiencing respiratory symptoms and instructing them to seek appropriate medical attention
- Reminding subject to contact the investigational site if they develop respiratory symptoms on the morning before a scheduled examination or if they have had changes to their health status

Upon arrival at the investigational site, subjects should be

- Assessed for fever
- Provided with PPE (e.g.; face masks)

Equipment that is meant to be used on more than one person should be draped to prevent possible contamination and appropriately cleaned before and after each use. Additional measures should also be considered such as:

- Posting guidelines
- Remind subjects of the need for social distancing/ consider having subjects wait outside of the investigational site (e.g.; in their vehicles until ready to be seen)
- Non-essential individuals accompanying study subjects should not permitted in patient areas

Trefoil Therapeutics, Inc.	Clinical Study Protocol TTHX-001
Confidential and Proprietary	Amendment 1.0: September 8, 2020

- Provide supplies for respiratory hygiene and cough etiquette, including 60-95% alcohol-based hand sanitizer (ABHS), tissues, no-touch receptacles for disposal, face masks, and tissues at healthcare facility entrances, waiting rooms, patient check-ins, etc.
- Provide respiratory hygiene supplies such as tissue to cover cough and hands-free receptacle for refuse disposal
- Remind subjects to wash hands and/ or use hand sanitizer

Study visits and assessments should be rescheduled at the discretion of the Investigator when there is a perceived increased risk to study subjects and/or investigational site staff.

